- If no response, then the research coordinator will make 3 attempts to call their emergency contact if they provided an emergency contact. Subjects will be asked to provide an emergency contact at the screening visit in case we cannot reach them because they moved, are in a hospital, etc. The emergency contact is usually someone that does not live with them, or at least someone with a different phone number.

This process will be initiated when the subject has not shown up to a study visit. If no response is received from the subject within 60 days of missing the study visit, the subject will be withdrawn from the study and considered lost to follow-up.

**Drop outs/Treatment failures:** Dropouts may occur due to participant choice or physician recommendation for reasons such as adverse effects, poor compliance, etc.

If a subject is randomized but misses Orientation, the instructors may offer the subject an individual Orientation session. If the subject is unable to complete Orientation before Class #2 after being randomized, they will not be permitted to continue in the study.

As soon as a subject is determined to be Lost to Follow-up, Withdrawn or Completed, all data collection will cease after collecting reasons for participant-initiated withdrawal on the Attrition Survey. The date a subject is no longer considered part of the study will be documented in an End of Trial form.

**Attrition Information:** CONSORT guidelines require a reason for dropout for every subject, and whether the reason was due to an adverse event. The research coordinator will collect attrition information for each dropout from the study, and record the dropout date, subjects' responses to Yes/No questions about general reasons for attrition that do not reveal the subjects' group assignment, and whether the dropout is Subject-initiated or Investigator-initiated.

If it is a Subject-initiated dropout or a lost to follow-up, the subject will be e-mailed a link to a REDCap Participant-Completed Attrition Information Survey consisting of one open

ended question to elicit feedback about their experience in the study and learn more about their reasons for not continuing in the study. As subjects' responses could reveal group assignment, the research coordinator and other blinded study team members will be blinded to subjects' responses to this survey in REDCap.

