### **Randomization Phone Call (by the SME instructor within 1-week before Orientation):**

At the end of the baseline visit, if a subject is deemed fully eligible for inclusion into the study, the research coordinator will inform the SME instructor, or other designated unblinded study team member, that the subject can be randomized during the week before Orientation. The SME instructor will disseminate the allocated randomized intervention to the subjects in their cohort, as the SME instructors are not blinded and they are not involved in the collection or analysis of study outcomes. During the Randomization phone call, the SME instructor will complete the following procedures to randomly assign the subjects in their cohort to one of two study groups (MBSR or SME) in REDCap:

- The SME instructor will call the subject in the week before the Orientation session.
  - If the SME instructor is unable to reach the subject for randomization, the SME instructor will email the subject to follow-up (See SME Instructor Email Template Randomization No Contact Made).
- The SME instructor will verify that the subject is still available for the study sessions. Subjects will be informed that they must attend the Orientation session to continue in the study. If they miss the Orientation session, and are unable to make up the Orientation before Class #2, they will not be able to continue in the study. If a subject thinks they will miss the Orientation, or if they think they will miss more than 2 classes during the first 8 weeks (including Class #1 to 8 and the Retreat), they will be encouraged to wait for another wave/cohort when they are able to make the time commitment. The SME instructor will not randomize any subjects who cannot commit, with reasonable certainty, to completing an Orientation session before Class #2, and at least 7 out of 9 classes during the first 8 weeks (including Class #1 to 8 and the Retreat).
- Upon confirming the subject's commitment to attendance and interest in participation, the SME instructor will select the randomization button in REDCap while they are still on the phone with the subject. Once the button is selected, the live feedback from REDCap will display the assigned group. In the same phone call (using a Randomization Script), the SME instructor will immediately inform the subject of the details of their group assignment, give them a brief pre-orientation of the program, and provide the subject with:
  - Welcome information

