**Attendance:**

The SME instructor for each cohort/wave will coordinate the documentation of attendance for each MBSR and SME subject in their cohorts throughout the 6 months that the subjects are in the study. Subjects’ attendance will be documented for the Orientation session, Class #1 to 8, the Retreat session, Booster sessions #1 to 4, and

any additional optional study booster sessions and retreat sessions that subjects participate in while they are in the study. Attendance will be recorded by the MBSR or SME instructor at the beginning of each Zoom session. For the purposes of this study, 'attendance' is defined as attending the class in full, entering the class late, and/or leaving the class early (e.g. partial attendance will count as full attendance).

**Within 24 hours of each session**, the SME instructors will record the attendance for each of the MBSR and SME subjects, in the Blinded Attendance Log in REDCap. Blinded study team members will be able to review the Blinded Attendance Log as it will not contain any information that would reveal group assignments.

Procedures for when a subject misses a session: The protocol for contacting subjects who miss a session will be similar for both MBSR and SME groups. The following procedures will be completed when a subject misses an MBSR or SME session that they are assigned to:

- If a subject misses the Orientation session after being randomized, the subject's instructor (either MBSR or SME) will contact the subject and offer them an individual Orientation session. If a subject does not complete Orientation after being randomized to MBSR or SME prior to Class #2, the SME instructor will notify the research coordinator and the subject will be withdrawn from the study.
- If a participant misses a Class #1 to 8 session, Retreat session or booster session, the subject's instructor (either MBSR or SME) will complete the following procedures:
  - Send a follow-up email if someone misses a class and let them know we missed them.
  - Encourage them to continue to follow along with the home practice and do their best to attend all the remaining sessions that they are assigned to.
  - Offer to be available by email, phone call, or schedule a time to meet usually before or after the next class, if they wish to have a private discussion.
  - The SME instructor will ask the MBSR instructor to let them know if they receive any communication from a study participant regarding a missed session.

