**Blinding:**

The PI, research coordinators and all other research team members involved in the collection or review of outcomes data will be blinded. The random assignment of subjects to MBSR or SME will not be communicated to any research team member who will be collecting or reviewing outcomes data. The subjects, SME instructors, MBSR instructors, data manager, video coders, [name] will be asked to keep the study group assignments concealed from the blinded investigators and study personnel.

The SME instructors, MBSR instructors, and other unblinded research team members will be asked not to reveal the number of study subjects in an MBSR course, or in an SME course, to the research coordinators and other blinded research team members.

The research coordinators and other blinded research team members will be:

- Blinded to the number of subjects randomized to MBSR in a cohort/wave
- Blinded to the number of subjects randomized to SME in a cohort/wave

The research coordinators and other blinded research team members will be:

- Aware of the total number of subjects randomized in a cohort/wave

Subjects will be asked to keep their study group assignment concealed from the blinded study personnel, including the research coordinators and other study personnel that they meet during the study visits. At the beginning of any phone call, study visit, or other contact with a subject, blinded research team members will remind subjects not to say anything that would reveal their group assignment e.g. instructors' names, specifics about their classes or Daily Diary survey questions, the PSU Zoom link for their classes, etc.

The research coordinators and other blinded research team members will not have access to the Experience Sampling Surveys in REDCap, which will be managed by unblinded research team members e.g. the SME instructors. Additionally, the PSU Zoom links for the classes will only be available to [name] and the instructors as these individuals will not be blinded.

Procedures in the MBSR group will parallel procedures in the SME group to maintain blinding. As an example, since subjects in the MBSR group are not allowed to continue with MBSR if they miss Orientation, the same will apply for subjects in the SME group. Additionally, if a session for one group needs to be canceled for any reason, the concurrent session for the other group will also be canceled.

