**MBSR Intervention and Stress Management Education (SME) control:**

Once subjects are assigned to a study group, they will participate in 14 MBSR or SME control sessions:

- Orientation session that will last 1 and a half to 2 hours depending on the duration of the individual participant interviews (1 session).
  - Subjects will be informed that they must attend the Orientation session to continue in the study. If a subject misses the Orientation session after being randomized, the subject's instructor will contact the subject and offer them an individual Orientation session. If a subject does not complete Orientation after being randomized to MBSR or SME, the SME instructor will notify the research coordinator and the subject will be withdrawn from the study.
- Class #1 to 8: These sessions are once a week during the first 8 weeks, starting approximately 1 week after Orientation. The duration for each of these sessions will be 2 and a half to 3 hours (8 sessions).
- Retreat: A single longer MBSR or SME session that will last 7 hours (1 session)
- Booster sessions #1 to 4: These are 45-minute long MBSR or SME sessions every month in Months 3, 4, 5 and 6 (4 sessions).

All MBSR and SME sessions will be delivered online by experienced instructors in a live interactive virtual classroom using videoconferencing (PSU Zoom). Participants will be asked to find a place in their homes where they will not be disrupted during the sessions.

MBSR and SME sessions will be held in small groups. The number of sessions will be the same in MBSR and SME to control for instructor attention and group support.

Attendance will be recorded at each session (See above section on Attendance). Subjects will be instructed to let their instructor know if they need to be excused from a session. It is possible that for some unforeseen reason a subject misses a session. If this happens, the subject may not be able to make the session up, but they will be encouraged to continue to follow along

with the home practice and do their best to attend all the remaining sessions that they are assigned to (See above section on “Procedures for when a subject misses a session”).

After Class #5: Subjects will be sent a link from REDCap to complete the MBSR or SME Midway Check-in form.

After Class #8: Subjects will be sent a link from REDCap to complete the MBSR or SME Final Class Assessment form.

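### Randomised subjects who miss Orientation lose outcome follow-up as well as their classes, which creates avoidable missing month-6 HbA1c and undercuts the intention-to-treat aim

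*Combined protocol and SAP*

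**What the plan says.** **Knowledge of arm.** In section 7.2.4 (Randomization Phone Call), which takes place in the week before Orientation, "the SME instructor will immediately inform the subject of the details of their group assignment" as soon as REDCap displays it.

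**The Orientation rule.** It appears in four places, in different words:
- Section 7.2.2 (Drop outs/Treatment failures): "If the subject is unable to complete Orientation before Class #2 after being randomized, they will not be permitted to continue in the study". On a make-up session it says only that "the instructors may offer the subject an individual Orientation session".
- Section 7.2.4 (Attendance): the make-up session is offered outright. If Orientation is not completed before Class #2, "the SME instructor will notify the research coordinator and the subject will be withdrawn from the study".
- Section 7.2.4 (MBSR Intervention and SME control): "If a subject does not complete Orientation after being randomized to MBSR or SME, the SME instructor will notify the research coordinator", followed by withdrawal from the study. This sentence has no Class #2 deadline.
- Section 7.2.4 (Blinding): "subjects in the MBSR group are not allowed to continue with MBSR if they miss Orientation", and the same is applied to SME. This wording concerns the programme, not the study.

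**What withdrawal means.** Section 7.2.2: "As soon as a subject is determined to be Lost to Follow-up, Withdrawn or Completed, all data collection will cease". The only exception is the reason given on the attrition survey.

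**The analysis.** Section 8.3 commits all primary analyses to intention-to-treat using the data on every randomised participant. Its examples include people who were randomised and left before beginning their allocated programme.

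**The concern.** The analysis plan names a group that it means to analyse, and the procedures ensure that this group has no outcome after baseline. The gap arises after randomisation, once the subject knows the arm, so the decision not to attend could depend on the arm. For these subjects the month-6 contrast, which is the primary one, rests on a missing-at-random assumption that the trial imposes on itself. If withdrawals differed by arm in number or in prognosis, the estimate would be biased.

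The rule also sits badly with other parts of the protocol:
- Section 3.3.1 lists the grounds for removal from the study: safety (PHQ-9, pregnancy, adverse-event review) and withdrawn consent. Missed Orientation is not among them.
- Section 7.2.2 (Investigator-initiated withdrawals) already distinguishes leaving the study from leaving the intervention.
- Section 9.3 and DSMP section IV.E state, in the setting of adverse events, that every subject is followed to 6 months.
- A subject who attends Orientation and then misses classes is encouraged to carry on (section 7.2.4, Attendance). No withdrawal rule for missed classes is stated.

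**Working it through.** **1. The plan's own figure.** Inputs from section 8.2: difference 0.5, SD 0.9, two-sided alpha 0.05, power 80%, mean group size 18, ICC 0.08, dropout 15%, 145 per arm.
- Design effect: 1 + (18 − 1) × 0.08 = 2.36. The printed formula has the bracket reversed and would give −0.36. The stated 2.36 is correct.
- A two-sample t-test needs 52 per arm. 52 × 2.36 = 122.7, and 122.7 / 0.85 rounds up to 145 per arm, or 290 in total. The stated figure reproduces and is not in dispute.
- Analysed per arm: 145 × 0.85 = 123.25.
- SE of the contrast: √(2 × 0.9² × 2.36 / 123.25) = 0.176. Power at 0.5 is 0.81. The significance limit is 1.96 × 0.176 = 0.345.

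**2. Possible bias.** The documents give no rate of Orientation non-completion, so the rates and departures below are assumptions. Let p be the proportion withdrawn in an arm, and d the departure, meaning the difference in mean HbA1c change between those withdrawn and those kept. A comparison of kept subjects is off by p₁d₁ − p₀d₀. Two-sided type I error is 1 − Φ(1.96 − bias/SE) + Φ(−1.96 − bias/SE).

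| Withdrawn (one arm v other) | Departure, both arms | Bias | Bias/SE | Type I error |
|---|---|---|---|---|
| 5% v 5% | 0.5 | 0 | 0 | 0.050 |
| 5% v 2% | 0.5 | 0.015 | 0.085 | 0.051 |
| 10% v 5% (about 14 v 7 of 145) | 0.5 | 0.025 | 0.142 | 0.052 |
| 10% v 0% | 0.5 | 0.05 | 0.284 | 0.059 |

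The 10% v 5% row is 0.025 / 0.5 = 5% of the target effect.

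**3. Departure needed to lose significance.**
- Observed 0.50: the margin over the limit is 0.155. A 5-point imbalance needs a departure of 0.155 / 0.05 = 3.1 points, and a 10-point imbalance needs 1.55.
- Observed 0.40: the margin is 0.055, and the figures are 1.10 and 0.55.

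**4. Power if these subjects are kept.** Suppose non-starters gain nothing and fall within the planned 15% loss, with the design effect unchanged.
- 5% of each arm (about 7 subjects): analysed n is 145 × 0.90 = 130.5, SE 0.171, expected effect 0.5 × 0.85 / 0.90 = 0.472, power 0.79.
- 2% of each arm: n 126.15, SE 0.174, effect 0.489, power 0.80.

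**The case against.** **The intention-to-treat promise is kept literally.** A reader might infer that the Orientation rule contradicts section 8.3. It does not do so word for word. Section 8.3 promises to include each randomised participant's data and does not promise a month-6 value. These subjects stay in their assigned arm through baseline HbA1c. This stands and limits the claim, but a baseline value alone adds almost nothing to the month-6 contrast.

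**The number should be small.** Availability is checked at pre-screening, screening, baseline and on the randomisation call. Subjects who cannot commit are not randomised, and a make-up session is provided for. This also stands. A reader might still infer that the primary test is materially compromised. Type I error reaches 0.136 only with 15% withdrawn in one arm, none in the other, and a departure of 1.0 point, and nothing in the documents points to that.

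**The rule is symmetric.** It is, and equal withdrawal with equal departure gives no bias. But a symmetric rule does not guarantee symmetric withdrawal when subjects know their arm. The documents do not show whether withdrawal would differ.

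**The purpose of the rule.** It is tempting to say that the rule serves blinding and does not need study withdrawal. The Blinding section cites the rule as an example of parallel procedures and gives no reason for it, so that argument cannot be made from the text. What can be said is that applying it to classes alone, in both arms, keeps procedures parallel.

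**Outside results are already collected.** The Table 3 notes and sections 7.2.3, 7.2.6 and 7.2.7 provide for recording outside HbA1c after a missed visit. None extends this to withdrawn subjects, for whom section 7.2.2 stops collection.

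**Spare numbers.** Sections 4.2.3 and 8.1 allow up to 320 randomised. At 320 with the same inputs, power is 0.847 with 15% loss and 0.80 with 25%. That largely covers precision but does not cure selective loss.

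**Conclusion.** The point holds in a limited form. As written, the plan creates avoidable missing month-2 and month-6 HbA1c in randomised subjects who know their arm. It does so by a rule that does not fit sections 3.3.1, 8.3 and 9.3, or the protocol's own distinction between leaving the study and leaving the intervention. This undercuts the intention-to-treat aim without breaking its wording.

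Bias is a risk and not a demonstrated fault. In the moderate scenarios it is 0.015 to 0.05 HbA1c points, with type I error of 0.051 to 0.059. Those figures rest on assumed rates and departures, on the section 8.2 inputs, and on other dropout being ignorable. The rule alone is unlikely to overturn an observed 0.50, but it could matter for a result near the significance limit. It is worth fixing because the remedy is cheap, not because the trial is in danger.

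Withdrawals for pregnancy or safety, the lost-to-follow-up process, and a general sensitivity analysis for missing data are separate matters and are not part of this point.

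**What to change.** 1. Reconcile section 7.2.2 and the Attendance and MBSR/SME passages of section 7.2.4 with sections 3.3.1, 8.3 and 9.3, the Blinding passage, and the investigator-withdrawal text. Missing Orientation should end class participation in both arms but not outcome follow-up. Use the same deadline and make-up wording throughout.
2. For these subjects only, make an exception to the cessation of data collection. Seek month-2 and month-6 HbA1c by home kit, remote visit or outside record unless they withdraw consent. All three routes are already in the protocol.
3. Report withdrawals before Class #2 by arm in the final analysis. Dropout dates and reasons are already recorded, so this needs no new data.

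**Cost.** Protocol wording, some coordinator calls and kits, and possibly consent wording for record look-up (the consent form was not available to check). There is a small loss of power if non-starters gain no benefit: about 0.81 to 0.79 if they are 5% of each arm. The diluted effect is the one that an intention-to-treat analysis sets out to estimate.

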### 7.2.3 Visit #1 (Baseline Study Visit)

Enrolled subjects who meet the eligibility criteria at the screening visit will be invited to schedule a baseline study visit at the CRC. If the baseline visit cannot be completed in the CRC due to COVID-19, or the preference of the subject, the baseline visit will be completed remotely using videoconferencing (PSH Teams), and all data that can be collected remotely will be obtained, including the home hemoglobin A1c using the Home A1CNow Self Check kit, urine pregnancy test when applicable, diabetes device data, and surveys. The subject will not participate in hair, nail or saliva collection if visits are remote. The baseline visit will last approximately 3 hours. The baseline visit will be scheduled within 6 weeks prior to the planned start of the study intervention (Orientation session). Eligible subjects who complete the baseline visit can undergo randomization and subsequently attend Orientation. Hemoglobin A1c and Perceived Stress Scale-10 assessments will be repeated at the baseline visit, however subjects will not be excluded at baseline based on the results. The MINI will not be repeated at baseline. Subjects will need to continue to meet the rest of the Inclusion/Exclusion criteria at the baseline visit to be able to continue in the study. An overview of the study procedures is found in **Table 3**.

Subjects will be asked to provide the following for their remote or in-person baseline visit:

- The completed Baseline Medical History questionnaire they were given at the screening visit; They will complete this electronically or on paper. If they complete a paper form, they will be asked to mail it back. They can also bring the paper form to their baseline visit if it is being done in the CRC.
- A list of their current medications and dietary supplements so their current medications and supplements can be recorded
- Their smartphone, if they have one
- Their diabetes devices (glucometers, CGM, insulin pump and other smart insulin delivery devices)
- Home A1cNow Self Check Kit if provided one at screening

The subjects will present to the baseline visit in the CRC in a 10-hour fasting state (no food or drink, except for water). Additionally, subjects will be instructed not to eat or drink (except for water), chew gum, smoke, brush their teeth, exercise physically, or consume prescription or over-the-counter medications in the 60 minutes prior to their baseline visit (as well as during the last 60 minutes of their baseline visit) as we will be collecting saliva samples 1) Just before the study visit starts, and 2) immediately after the study visit ends. If subject forgets to fast, blood will still be drawn and documentation will be made of how many hours it has been since they last had something to eat or drink.

Subjects will be instructed not to wash their hair for 24 hours before their study visit in the CRC and not to have their hair cut to a length less than 2 cm (as we will be collecting *optional* 2 cm hair samples weighing at least 10 mg to assess cortisol levels over the past 2 months). Subjects may opt-out of this procedure and will still be permitted to continue in the study. Subjects will be instructed not to clip their fingernails for at least 2-3 weeks prior to their study visit to allow for the *optional* clipping of approximately 2 mm of nails from each finger of both hands.

Subjects will be instructed to remove any nail polish at least 24 hours before their study visit. Subjects may opt-out of this procedure and will still be permitted to continue in the study.

At the baseline visit, subjects will be given another copy of the Class Schedule and Homework. The research coordinator will verify that the subject continues to be available for the intervention sessions with reasonable certainty. If a subject thinks they will miss the Orientation, or if they think they will miss more than 2 classes during the first 8 weeks (including Class #1 to 8 and the Retreat), they will be encouraged to wait for another wave/cohort when they are able to make the time commitment.

The research coordinator will obtain baseline measures including saliva, blood, hair (optional), and nail (optional) samples for hormonal and metabolic parameters, and a brief physical exam if the baseline study visit is in the CRC.

Self-administered questionnaires will be directly entered into REDCap by all subjects and reviewed by the research coordinator for completeness. Data will be collected from subjects' diabetes devices (glucometers, CGM, insulin pump and other smart insulin delivery devices) if they use these devices.

At the baseline visit, a urine pregnancy test will be administered to female subjects of childbearing potential who do not meet any of the criteria for reasonable certainty of not being pregnant as defined above in the screening visit. Any subjects found to be pregnant will be informed of their pregnancy test results, and then withdrawn from the study due to the effects of pregnancy on study outcomes. If the subject has a pregnancy test within 2 weeks before the baseline visit, documented in their screening visit or verified in their medical records, the pregnancy test result can be accepted in lieu of repeating the test at baseline. If the study visit is conducted remotely, and if a pregnancy test result collected within 2 weeks before the study visit is not available, then the subject will be mailed a urine pregnancy test to complete at this visit. Subjects will communicate their urine pregnancy test result to the study team by showing the research coordinator their pregnancy test result as displayed on their urine pregnancy test kit during the (PSH Teams) live videoconferencing study visit. If the pregnancy test is positive, the subject will be withdrawn from the study.

Subjects will be given a Home A1CNow Self Check kit at baseline, or if they received a kit at screening they will be asked to bring the kit to their remote or in-person baseline visit. If the baseline study visit is conducted remotely, subjects will be mailed the Home A1cNow Self Check Kit. The research coordinator will review procedures and watch instructional videos with subjects, and assist the subjects in obtaining their hemoglobin A1C value from the kit. Subjects who complete their baseline study visit in the CRC will bring this kit home in case, for any reason, they are not able to return to the CRC for their 2 month and 6 month visit so that they will be able to collect their hemoglobin A1C results at home as this is the primary outcome for this study. If the 2 month and 6 month visits are being conducted at the CRC, the subjects will be asked to bring their Home A1CNow Self Check kit to the CRC and the kit will be used to collect their home hemoglobin A1c, in addition to the blood draw for hemoglobin A1c. The Home A1cNow Self Check Kit contains step by step instructions for subjects to reference for future testing.

If the subject opts-in to wearing an Actigraph device, the subject will be given an Actigraph device to wear around their waist for 7 days after the baseline visit. If the study visit is conducted remotely, the subject will be mailed the Actigraph device, with a stamped envelope to return after the required wear time.

